6.0 Study Design and Procedures

- This study will be a randomized controlled design.
- During the telephone screening, all the participants will be asked to choose a group that
 they prefer to participate which includes 3 options: Group 1: In-person assessments
 and in-person training; Group 2-In-person assessments and online training and Group
 3- Online assessments and online training.

[figure not shown]

- Figure 1 above shows recruitment and distribution of participants into differenct groups based on the options given for assessment and training to the participants during telephone screening.
- After the participants are allocated to groups 1,2 and 3 depending on their choice, each
 participant from every group will be randomly assigned either Group A (CogXergaming)
 or Group B (Matter of balance) for training by flipping a coin.
- Al the participants will be undergo 1-on-1 testing and training.
- Study protocol will vary according to the groups that the participants choose to be in (Groups 1,2 or 3).
- For Group 1 (In-person assessments and in-person training): Group A (CoXergaming) will undergo a total of 8 weeks session with first week and last week comprising of assessment. 6-week training will be delivered using the Nintendo Wii-Fit gaming system and a pointer mouse. Participants will visit the laboratory 3 times a week for 6 weeks with each session lasting for 60 minutes (18 training sessions). During training session, participants will wear a gait belt and will be guarded by a research assistant for safety. On the other hand, if the Group 1 participant gets assigned to Group B (Matter of balance) then participants from Group B will undergo a total of 10 weeks session with first week and last week comprising of assessment. The participants will undergo an 8-week (one session a week for 2 hours/day, 8 sessions in total) structured intervention specifically designed to reduce the fear of falling and to increase the engagement in PA.

| Test | Pre- test | CogXergaming/TeleXercise Intervention (6 weeks) | | | | | | | | | | | Post-test | | | | | | | |
|---------|--------------|---|---|---|---|---|---|---|---|---|----|----|-----------|----|----|----|----|----|----|-----|
| Session | 1-4 | 1 | 2 | 3 | 4 | 5 | 6 | 7 | 8 | 9 | 10 | 11 | 12 | 13 | 14 | 15 | 16 | 17 | 18 | 1-3 |
| Week | 1 | 2 | | 3 | | 4 | | 5 | | 6 | | | 7 | | | 8 | | | | |

| Test | Pre-test | M | latte | Post-test | | | | | | |
|---------|----------|---|-------|-----------|---|---|---|---|---|-----|
| Session | 1-4 | 1 | 2 | 3 | 4 | 5 | 6 | 7 | 8 | 1-3 |
| Week | 1 | 2 | 3 | 4 | 5 | 6 | 7 | 8 | 9 | 10 |

Protocol design

- For Group 2 (In-person assessments and online training): The assessments will be performed same as Group 1 (in-person). For training sessions, Group A (CoXergaming) will be trained through TeleXercise intervention via zoom online application (details are provided in the intervention section) for 6-weeks. All participants will be undergoing 3 training sessions per week for 6 weeks (18 training sessions). Group B (Matter of balance) will also be trained online and will undergo an 8-week (one session a week for 2 hours/day) structured intervention specifically designed to reduce the fear of falling and to increase the engagement in PA.
- For Group 3 (Online assessments and online training): The assessments will be performed online during the first and the last week. The online pre and post

assessments would consist of assessing balance, gait, cognitive performance and physical activity online via zoom application (details provided in outcomes). For the training sessions, Group A (CoXergaming) will be trained through TeleXercise intervention via zoom online application (details are provided in the intervention section) for 6-weeks. All participants will be undergoing 18-training sessions over a period of 6 weeks. Group B (Matter of balance) will also be trained online and will undergo an 8-week (one session a week for 2 hours/day) structured intervention specifically designed to reduce the fear of falling and to increase the engagement in PA.

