can do the 1-on-1 training online at home via zoom application); Group 3: Online assessments and online training (where all the tests and training will be conducted online via zoom application). Those who choose to be in Group 1 or Group 2, they will be screened for claustrophobia using the claustrophobia questionnaire (Napp, A. E. et al 2016) and individuals who score an average of 1.2 or less will be given the option of being included for fMRI study participation. Once he/she meets the inclusion criteria, they would be scheduled for an in-person laboratory screening at Room 415, B56 or 725 of the College of Applied Health Sciences building. The laboratory screening involves evaluating the individual's performance on various clinical measures balance, muscle strength, endurance and cognition. The participants will also undergo osteoporosis screening using an ultrasound device to measure their heel bone density. During the bone density testing, their heel will be squeezed by the rubber membranes of the testing apparatus. As a result, they will experience some pressure, and/or mild tingling, cold or warm sensation on the heel from the membranes or the gel used during the testing. While Group 3 will continue with online test measures followed by training sessions.

All participants' information will be recorded in a database in the form of an excel sheet that will include the information of the participants eligible and those not eligible for study. For participants not eligible for the study, the reason for withdrawal or exclusion from the study participation as per the telephonic interview will be recorded. An excel file would be maintained to document the results of participants' initial telephone screening, osteoporosis screening, clinical assessment and laboratory dynamic stability test.

To minimize coercion and undue influence on the participants, the potential participants will directly call research coordinators in response to a flyer and/or other recruiting materials or by word of mouth. In case of interested participants referred by the physician or met at recruitment meetings, the researcher will collect the contact information and will initiate contact to perform a telephonic screening. Participation is voluntary and individuals' decisions will not be influenced by research personnel who conduct pre- or post-training assessments.

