- Participants will not proceed with the study if any of the following occurs at baseline measurement: 1) HR > 85% of age-predicted maximal heart rate (HRmax) (HRmax = 220 age), 2) systolic blood pressure (SBP) > 165 mmHg and/or diastolic blood pressure (DBP) > 110 mmHg during resting), and/or 3) oxygen saturation (measured by pulse oximeter) during resting < 90% (only for participants who choose to go for inperson assessment and/or training). For The blood pressure criteria is only for participants who choose to go for in-person assessment and/or training which will be measured in laboratory (Group 1 and 2). To serve good for safety in group 3 (online assessment and online training), we will mail O₂ saturation monitors along with heart rate monitors. Participants will not proceed with the study if at baseline measurement HR > 85% of age-predicted maximal heart rate (HRmax) (HRmax = 220 age) (only for participants who choose to go for online assessments and/or training). If excluded and the participant wants to participate in the study, they would need to obtain a physician consent.
- Unable to stand for 5 minutes without an assistive device (length of a Wii Fit game)
- Uncontrolled acute medical/surgical, neurological or cardiovascular disease
- History of bone fracture or significant other systemic disease or surgery in the last six months
- Moderate to severe cognitive impairment (MOCA <24/30)
- Specific to MRI participants: Self-reported presence of pacemaker, metal implants other than orthopedic implants, and/or Claustrophobia, cataract surgery (lens not compatible to the MRI confirmed by the MRI technician)
- Do not have either a desktop computer/laptop/tablet with access to internet (only for participants who choose to go for online assessments and/or training)
- Do not have a helper buddy to assist or provide physical support (only for participants who choose to go for online assessments and/or training)
- Participants who cannot understand and communicate in English will be excluded due to instructions for training and protocol being provided in English.

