
Group A – CogXergaming in the form of TeleXercise intervention
[For Group 2 (in-person assessments and online training) & Group 3 (online assessments and online training)]

The TeleXercise intervention proposes to deliver exercises via exergaming-based animation videos combined with or without explicit cognitive exercises delivered by a research personnel monitoring the intervention. All the online training sessions will be carried out on one-on-one basis. Participants will need a desktop computer/tablet or smart phone of their own with access to internet on which the commercially available application will be installed. Research personnel will set up meeting invites and send them links via their preferred receiving mode (SMS or email). Once the research personnel admits all participants into the room via the secure link the research personnel will start the intervention. The research personnel will launch the Mimic-Game-&-Groove application on their computer and share their screen with the participants. Participants have to turn their videos on for the research personnel to see them. The audio will be kept in mute by the health coach and once the participant tries to talk or show any discomfort he/she will unmute in any unanticipated event. The intervention consists of participants mimicking the exercises that are shown in form of games and dances on their screen (similar to exergaming but being passive rather than interactive). The participants will not receive knowledge of performance or knowledge of results like in traditional exergaming; however, after each session, they will receive a brief feedback by the health coach, 1) qualitative based on the movements, 2) quantitative based on their heart rate max (intensity achieved) and the number of steps per session (measured via wearable sensors/smartphone). Participants will receive the TeleXercise intervention for three times per week for 6 weeks (18 sessions) with each session lasting about 1 hour and 30 minutes, including warm-ups, rests, and a cooldown. Training will consist of 20 minutes of warm-up -joint mobility, walking, and stretching exercises of moderate intensity, and cool-down- low-intensity stretching exercises and 1 hour of TeleXercise. A wearable device provided will measure the heart rate and physical activity during the course of training. They will be asked to read out the Heart rate and number of steps before the training begins (which will be displayed on the wearable device). Furthermore, after each set of exercise, they will be asked to note down their heart rate and number of steps displayed on their watch and when asked they should report it to the research personnel. Participants must be below 85% of the age predicted maximum heart rate to continue testing and training. All participants will be provided with a feasibility questionnaire and their compliance will be recorded at the end of the 4 weeks of training. Participants are provided with a set of balance exercises, which are demonstrated via animated avatars. The balance exercises includes non-interactive balance games (stepping forward, backward, sideways), Tai-Chi, Weight shifting (to right leg, left leg and practice distributing equal weights on both the legs), Aerobic (stepping in place), dance, strength, and stretching. Please see the figure below

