6.3 Safety

Safety during in-person procedures: Participants will be wearing a safety harness system during the laboratory pre- and post-tests performed on motorized equipment such as the Balance Master and treadmill. For clinical tests, participants will be secured with a gait belt and will be allowed to use their assistive device (if using one) with close monitoring by the researcher or clinician. During the training sessions, the participants will also wear a gait belt, and external assistance (contact guard support) will be given for safety.

Safety during online procedures: Participants will be provided with a heart-rate, oxygen saturation and physical activity monitor which will be mailed to them after telephone screening. To further ensure safety, 2 additional steps will be followed prior to participation in the study:

- 1) If the participant's resting O2 saturations is < 90% and heart rate is >85% of age predicted maximal heart rate, they will be excluded or given the option of obtaining physician consent to be included in the study. The health coach will monitor participant's resting heart rate and O2 saturation at the beginning of every testing/training session and at regular intervals during the training.
- 2) We will remotely administer 2-min walk test (shortened version of 6 min walk test) during the online assessment session for Group 3 (online assessment and online training). In this test, participants will march in spot or around the room (with health coach able to see them on the screen) in front of the health coach for 2 minutes with the pulse oximeter on. On completion, the health coach will obtain the heart rate and oxygen saturation. If the HR exceeds 85% of age appropriate HR max and O2 saturation falls below 90% then they will be excluded from the study. For the testing procedure as well as the training procedure research personnel will engage with one participant only. During every zoom meeting, participants will not

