scores will be generated accordingly which can then be exported via excel sheet. 1) Picture sequence memory test: This test evaluates the episodic memory of the individual. The participant recalls a series of pictures in a particular manner described before. For example, the participant is shown pictures about how to go camping. A series of pictures are shown on building a tent to fishing. For the test, the pictures are jumbled, and the participant is expected to place those pictures in the same order described. The number of adjacent pairs of pictures placed correctly will score a point. The scores are application generated. 2) Flanker inhibitory control and attention test: In this test, the individual is instructed to click on the arrow on the keyboard that matches the direction of the middle arrow in the stimulus given on the screen. Accuracy of the responses are recorded, and the scores are application generated. 3) List Sorting Memory test: The test is divided into two subsets to evaluate working memory. The participant will be shown a picture of animals. For the first subset, the task for the participant is to name the animals from smallest size to the largest size. The second subset involves a category of food along with pictures of animals. The task of the participant is to say the food first and then name the animals from smallest size to the largest size. The accuracy of the participants' response will be recorded by the application. 4) Dimensional Change card sort: This test involves three subsets assessing executive functioning. For the first subset, the participant is expected to choose the same shape of the stimulus provided, for example, if the stimulus given is a boat, and for the answers from which the participant is supposed to choose is given as rabbit and boat, he is expected to click on the boat. In the second subset, the participant is expected to click on the object that matches the color of the stimulus and avoid clicking on the same shape. The last subset involves playing the first and the second subset together in a randomized order generated by the application. 5) Pattern comparison Processing speed test: This test involves the participant to hit the yes or no button depending on the pictures provided look the same or not. Similarity of shapes of objects, colors are provided as stimulus. This test evaluates the processing speed of cognitive functioning.

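### The A/B coin toss has no stated timing, operator or log, so it may come before eligibility is final and could not be audited

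*Combined protocol and SAP*

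**What the plan says.** Section 6.0 gives the only rule for allocating A or B. Participants choose Group 1, 2 or 3 at telephone screening. Each is then assigned, within the chosen Group, to Group A "or Group B (Matter of balance) for training by flipping a coin". The schedule tables in 6.0 place the pre-test in week 1 and training from week 2 for both arms, but they do not place the toss. Sections 9.0 and 12.0 add nothing on allocation.

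Several steps that decide who stays in the trial can come after the telephone call:

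- Section 5.0: those choosing Group 1 or 2 who pass the call have a further step, "they would be scheduled for an in-person laboratory screening".
- Section 6.1: grip strength is an inclusion criterion measured only in people who attend in person.
- Section 6.1: "Participants will not proceed with the study if any of the following occurs at baseline measurement", followed by heart-rate, blood-pressure and oxygen-saturation limits, with a way back: "If excluded and the participant wants to participate in the study, they would need to obtain a physician consent".
- Section 6.3, online procedures: participants beyond the resting limits "they will be excluded or given the option of obtaining physician consent to be included in the study". Sections 6.1 and 6.3 also exclude on a 2-minute stepping or walking test.

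On records, Section 5.0 lists telephone screening, osteoporosis screening, clinical assessment and laboratory stability results. For people found ineligible, "the reason for withdrawal or exclusion from the study participation as per the telephonic interview will be recorded". Section 8.0 promises a codebook and database. Section 11.0 commits to monitoring reasons for drop-out. Section 12.0 expects 96 analysed, 16 in each of six subgroups.

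**The concern.** The two programmes are plainly different: 18 sessions over 6 weeks against 8 sessions over 8 weeks. Participants and staff may therefore have a preference. If the arm is known before eligibility and baseline are settled, then exclusion, re-entry by physician consent or a decision not to continue could depend on it, and the arms would no longer be comparable. Aim 1 is an A-versus-B comparison, and Section 12.0 intends the results to plan a larger trial, so a distortion would carry forward.

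The second issue is audit. Without a dated assignment, the name or role of whoever made it, and a count by arm of those lost after it, nobody could later show that the toss came after eligibility or that it was made only once.

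**Working it through.** **1. Order of events.** The stated sequence is telephone call, Group choice, then toss. The further sequence is telephone call, laboratory screening or online testing, baseline stops, possible re-entry, then training. No readable text links the two sequences. The toss could fall directly after the call or directly before training, and both fit the words. The caption of Figure 1 refers to distribution by assessment and training option; the figure itself cannot be read, so it may or may not settle the order.

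**2. The plan's own figures.** 120 enrolled × (1 − 0.20) = 96 analysed, and 96 / 6 = 16 per subgroup. Both reproduce. The 16 requires equal Group choice and an even split within each Group, and neither is controlled:

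- Group choice: at an assumed 60/36/24, the mean analysed per subgroup is 60 × 0.8 / 2 = 24, 36 × 0.8 / 2 = 14.4 and 24 × 0.8 / 2 = 9.6. This is the same under a coin or a blocked list.
- Coin: with an assumed 40 per Group, P(24:16 or worse) = 2 × P(Bin(40, 0.5) ≥ 24) = 0.268 in one Group, and 1 − (1 − 0.268)³ = 0.61 in at least one of three.

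**3. Precision lost to the coin.** For a Group of n, the mean efficiency relative to an even split is E[4A(n − A)/n²] = 1 − 1/n. The loss is 1/24 = 4.2% at n = 24, 1/40 = 2.5% at n = 40 and 1/60 = 1.7% at n = 60. This is minor.

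**4. Size of a possible bias (all inputs assumed).** The documents give no number excluded after the call. Suppose a fraction x of one arm only, those worst on a factor unrelated to the measured baseline value, is excluded once the arm is known, and that the factor correlates r with the outcome. The shift in the A−B difference is r × φ(z)/(1 − x), where z is the normal quantile at x.

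| x (of 60) | φ(z)/(1 − x) | r = 0.3 | r = 0.5 |
|---|---|---|---|
| 5% (3) | 0.109 | 0.033 SD | 0.054 SD |
| 10% (6) | 0.195 | 0.059 SD | 0.098 SD |
| 20% (12) | 0.350 | 0.105 SD | 0.175 SD |

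A simulated ANCOVA agreed to within 0.005 SD. For scale, with 48 against 48 and an assumed baseline-to-outcome correlation of 0.5, the standard error is √[(2/48) × (1 − 0.25)] = 0.177 SD. If exclusion depended only on the measured baseline value, a linear ANCOVA would largely remove the shift.

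**5. Where outcomes can be pooled across Groups.** Table 1 in 6.4 gives Group 3 different balance, gait and cardiovascular tests from Groups 1 and 2. For cognition it lists the same batteries. The text describes 7 + 5 = 12 battery and toolbox tests in person and 6 online, and three of those six (Flanker, card sort, pattern comparison) change from a click or key press to speech. In the in-person Flanker test, for example, "the individual is instructed to click on the arrow on the keyboard that matches the direction of the middle arrow", whereas online the answer is spoken. That six are described does not prove that only six are given.

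**The case against.** A reader might infer that the toss is made before baseline and that selection has been built into the design. The documents do not support that. No text places the toss before laboratory screening or baseline testing, and Figure 1 might place it after.

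A reader might also infer that a coin is an inadequate method. It is not: a fair coin has no stored sequence to foresee, and it is already tossed within Group. An unblocked list by Group would give the same distribution of splits, and permuted blocks add a predictability that the coin lacks. The gain comes from concealment until release, from timing and from the log.

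The room for discretion is limited. Most baseline stops are numeric. The physician-consent option in 6.3 is worded as needing both low saturation and a high heart rate at rest, which should be uncommon. The judgement about other significant systemic disease may well be made on the telephone. The re-entry route in 6.1 is broader, however, and any participant may still withdraw.

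Nor is it right that nothing is recorded. Section 11.0 monitors reasons for drop-out and provides for twice-yearly written reports, and the database may hold the arm. What these do not describe is a dated assignment or a count by arm of exclusions after allocation.

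Finally, this is a pilot without a power target, and the bias scenario is one-sided and wholly assumed. That limits the weight of the point but does not answer it.

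**Conclusion.** The point stands as a gap in timing and auditability, with moderate confidence. As written, the toss may come before final eligibility, and the records described would not show whether it did. It is not shown that this happens or that any bias exists.

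The range of 0.03 to 0.18 SD rests on assumed exclusion of 5 to 20% of one arm only and an assumed correlation of 0.3 to 0.5. Only at its extreme does it match the assumed standard error. Lost precision is not the reason to change. The figure of 16 per subgroup is arithmetically correct as an average under equal Group choice, but the design does not secure it. The change should be made before enrolment, because analysis cannot restore concealment once it is lost.

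**What to change.** In Section 6.0, replace the coin with a concealed, computer-generated 1:1 assignment within Groups 1, 2 and 3. It should be held by someone outside recruitment and assessment, or in a locked electronic system. Release each assignment, and log its date and who released it, only after eligibility and baseline testing are complete. Report any later exclusions by arm. Blocking is optional; if used, block sizes should vary and stay undisclosed. Without blocks, chance imbalance within a Group remains.

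In Section 12.0, include Group as a factor in the ANCOVA for outcomes measured the same way across Groups, and analyse Group 3 separately where its tests differ. Restate the sample size as about 96 analysed in total, with 16 per subgroup only an average if Group choice is equal. Separately from the coin, the online form of Group A training is described as "similar to exergaming but being passive rather than interactive", so it would help to show A−B estimates by Group beside any pooled one.

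The cost is a list or system, a holder, and a few sentences; the total of 120 is unchanged. The practical downside is that training slots cannot be booked by arm until baseline is complete. Both schedules begin with a pre-test week before training, so the arm is not needed earlier for the visits they show.
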